**PROTOCOL OF A THESIS FOR PARTIAL FULFILMENT OF
MASTER'S DEGREE IN ANESTHESIOLOGY, INTENSIVE CARE AND PAIN
MANAGEMENT**

Title of the Protocol

***Ultrasound-Guided Modified Pectoral Plane (PECS II) Block versus
Erector Spinae Plane Block (ESPB) for Postoperative Analgesia of Modified
Radical Mastectomy***

Post-graduate Student: [name].

Degree: M.B, B.Ch., Faculty of Medicine, Ain-Shams University.

NCT: NCT06714682

DATE OF DOCUMENT: 1/8/2024

**Faculty of Medicine
Ain Shams University
2024**

What is already known on this subject? What does this study add?

Modified Radical Mastectomy (MRM) is a surgical procedure that removes the entire breast, including the skin, breast tissue, areola, and nipple, along with most of the axillary lymph nodes. However, most of the chest muscles are left intact. It is a less invasive surgery than a radical mastectomy, which also removes the chest muscles. It is a standard option for treating breast cancer that has spread to the axillary lymph nodes.

Postoperative pain in MRM is a common problem that can affect the quality of life and recovery of patients. Postoperative pain management is becoming an integral part of anesthesia care. Optimal pain control in patients undergoing MRM is imperative for good rehabilitation and functional outcomes. Current modalities in use aim to reduce postoperative opioid consumption to control postoperative pain thus minimizing its side effects in what is recently known as multimodal analgesia techniques.

Regional blocks have been introduced for postoperative pain relief such as thoracic epidural block (TEB), thoracic paravertebral block (TPVB) and intercostal blocks. The use of ultrasound guidance has much improved the success rate of the nerve blocks and the development of new techniques.

Newer pain control modalities have been used providing adequate pain relief, not affecting muscle strength and utilized as excellent solutions for multimodal analgesia peri-operatively. Examples of these modalities are serratus anterior plane (SAP) block, pectoral nerve (PECS) block and erector spinae plane block (ESPB).

In this study we will compare the analgesic efficacies of modified pectoral plane (PECS II) block versus erector spinae plane block (ESPB) after MRM surgery.

1. INTRODUCTION / REVIEW:

Breast cancer (BC) is the most common type of female cancer in Egypt with an age-specific incidence rate of 48.8/100,000. Although incidence rate in Egypt is lower than the global figures, mortality is higher at an age-standardized rate of 20.4/100,000 compared with the US rate of 12.3/100,000 and the developed countries' rate of 12.8/100,000 (*Sung et al., 2021*) (*Globocan, 2020*).

It is the most commonly diagnosed cancer worldwide, with estimated new cases exceeding 2 million in 2020. Furthermore, it represents the leading cause of cancer death in women, with more than 680,000 deaths (*Sung et al., 2021*).

During MRM, some of the nerves in the chest are affected so most women have some level of pain in the days after the procedure. Severe acute postoperative pain following breast surgery is an independent risk factor in the development of chronic post-mastectomy pain (*Bakeer et al., 2020*), not only increasing the risk of persistent agony and prolongs hospitalization, it also affects recovery and increases healthcare costs (*Deng et al., 2020*).

Multimodal techniques for pain management have been recommended by the American Society of Anesthesiologists (ASA) for the management of acute postoperative pain (*Apfelbaum et al., 2012*) (*Nagaraja et al., 2018*). These techniques include oral analgesics as opioids, paracetamol and nonsteroidal anti-inflammatory drugs (NSAIDs) (*Nagaraja et al., 2018*), intravenous (IV) and regional analgesia. Inappropriate postoperative analgesia may increase morbidity and mortality (*Blanco R, 2011*).

PECS-II block is an interfascial plane block in which local anesthetic is injected between serratus anterior and pectoralis muscles that blocks the pectoral nerve as well as the long thoracic, intercostobrachial and lateral cutaneous branches of the inter-costal III, IV, V, and VI nerves. PECS-II is a less invasive and easier to be performed alternative to thoracic paravertebral block (TPVB). This block, defined by *Blanco et al.*, provides safe and adequate post-operative analgesia in the anterior chest wall after breast surgery. The most common complications are pneumothorax, vascular puncture, infection, local anesthetic systemic toxicity (LAST), allergy and failed block (*Blanco et al., 2012*) (*Wang et al., 2018*).

ESPB is a paraspinal fascial plane block in which local anesthetic is injected between the tip of the transverse process of the spine and the anterior fascia of the erector spinae muscles blocking the dorsal and ventral rami of the spinal nerves, as well as the sympathetic chain, resulting in analgesia of chronic thoracic neuropathic pain, breast and upper abdominal surgeries. The block, defined by *Forero et al.*, can cover several spinal nerve levels above and below the injection site as the local anesthetic spreads along the fascial plane, depending on the volume and concentration of the local anesthetic (*Forero et al., 2016*) (*Bonvicini et al., 2017*) (*Chin et al., 2017*). The main advantages of this technique include the ease of performing it, the analgesic efficacy and the low risk of complications as Pneumothorax, hemidiaphragmatic paralysis, motor weakness, and neurological findings related to local anesthesia toxicity (*Tulgar et al., 2019*).

2. AIM / OBJECTIVES:

This study aims to compare the analgesic efficacies of the modified pectoral plane block (PECS II) and the erector spinae plane block (ESPB) after modified radical mastectomy surgery.

3. METHODOLOGY: Patients and Methods

- **Type of Study:** Prospective randomized comparative clinical study.
- **Study Setting:** Ain Shams University Hospitals, Cairo, Egypt.
- **Study Period:** 6 months to 12 months, starting from approval of the protocol, both from scientific and ethical committee.
- **Study Population:**
 - **Inclusion Criteria:**
 - 1- Female patients scheduled for MRM.
 - 2- Age eligible ≥ 40 & ≤ 65 yrs.
 - 3- Patients with American Society of Anesthesiologists (ASA) physical status I, II who will be scheduled for MRM surgery.
 - **Exclusion Criteria:**
 - 1- Age < 40 & > 65 years old.

- 2- Declining to give written informed consent.
- 3- History of allergy to the medications used in the study.
- 4- Contraindication to regional anesthesia [including coagulopathy (platelet count \leq 80,000, INR \geq 1.5) and local infection].
- 5- Severe hepatic impairment (INR \geq 1.5, Bilirubin \geq 2, Albumin \leq 2).
- 6- Renal dysfunction [GFR $<$ 50 ml/min calculated by MDRD (Modification of diet in renal disease) equation for GFR estimation (*Livio et al., 2008*)].
- 7- Psychiatric disorder.
- 8- Pregnancy.
- 9- Patient with history of thoracic spine surgery.

- **Sampling method:** Simple random sampling.
- **Sample Size:**

Using PASS 15 program for sample size calculation, setting power at 90% and alpha error at 0.05 and according to "***Bakeer & Abdallah, 2022***", the expected median VAS score 1-hour post-operative in PECS II group = 1(1-2) and in ESPB group= 2(1-3). Sample size of 10 patients per group will be needed to detect the difference between two groups.

- **Ethical consideration:**

Patient informed written consent and approval of the Research Ethical Committee of the Faculty of Medicine; Ain Shams University will be obtained before patient's allocation.

- **Study procedures:**

- **Preoperative settings:**

All patients will be assessed preoperatively by careful history taking, full physical examination, laboratory evaluation and other appropriate investigations.

At the preoperative visit, all patients will be instructed on how to evaluate their own pain by using a 10-cm visual analogue pain scale (VAS) (0 = no pain, 10 = maximum pain imaginable).

The nerve block will be performed in the preoperative block area following standardized monitoring, including non-invasive blood pressure (BP), electrocardiogram (ECG), and pulse oximetry (PO). Oxygen 2–3 L/min will be applied through the nasal cannula and IV midazolam 0.025 mg/kg will be given and dose may be repeated every 3–5 minutes until

sedation is adequate and patient still arousable up to 20 mg (*Pedro et al., 2022*). All blocks will be performed by the same two experienced senior attending doctors in ultrasonic-guided nerve blocks. Patients will be randomly divided according to a computer-generated random number table into two groups:

- Group 1 (**PECS II group**): patients will receive ultrasound guided PECS II block (10 patients).
- Group 2 (**ESPB group**): patients will receive ultrasound guided erector spinae plane block (10 patients).

Both blocks will be performed under complete aseptic precautions using ultrasound machine with high-frequency linear probe covered with sterile sheath (Sonosite M-turbo c, Bothell, Washington, USA) and linear ultrasound probe (2.5-7.5MHz) and a 22G 100 mm echogenic needle (B-Braun Medical Inc., Bethlehem, PA, USA) which will be inserted after standard skin disinfection and infiltration of 2 millilitres (mL) lidocaine 2% subcutaneously.

Pre-operative chest ultrasound will be done by the anesthesiologist to detect complications after puncturing of the blockade (hematoma in the puncture site by direct visualization and pneumothorax by Barcode/Stratosphere sign).

➤ **In the PECS II group: -**

The patient will lay supine with the ipsilateral arm abducted and externally rotated and the elbow flexed at 90 degrees. The high-frequency linear probe will be placed transversely between the clavicle medially and above and the shoulder joint laterally. After identifying the pectoralis major and minor muscles and the plane between them, the probe will be angled caudally to look for the pulsating pectoral branch of the thoraco-acromial artery; if it couldn't be found, the probe will be pushed 1-2 cm caudally and medially. In a caudal tilt, within a biconvex space, the artery will be recognised. After that, the block needle will be inserted in an in-plane approach to the artery's location and 10 mL of 0.25% bupivacaine will be administered (*Pani et al., 2019*). Then probe will be moved laterally and caudally towards the anterior axillary fold until the serratus muscle appears beneath the pectoralis minor muscle attaching to the underlying ribs. The third and fourth ribs will be detected. The needle will target the plane

between pectoralis minor and serratus muscles at the level of the third rib, followed by negative aspiration into the fascial plane then injection of 10 mL of 0.25% bupivacaine (*Alshawadfy and Al-Touny, 2023*).

➤ **In the ESPB group: -**

The block will be performed with the patient in a sitting position (*Costache, 2016*), The high-frequency linear probe will be placed in a longitudinal orientation 3 cm from the midline. Once the erector spinae muscle and the transverse processes identified, the block needle will be inserted in a caudad-to-cephalad direction until the tip lay in the interfacial plane deep to the erector spinae muscle, 20 mL of 0.25% bupivacaine will be administered for block performance (*Forero et al., 2016*).

• **Intraoperative settings:**

On arrival of the patients to the operative room, ECG, non-invasive blood pressure, pulse oximetry will be applied with capnography during ventilation till extubation. Baseline parameters such as systolic blood pressure (SBP), diastolic blood pressure (DBP), mean blood pressure (MBP), heart rate (HR), and arterial oxygen saturation (SpO₂) will be also recorded.

Before surgery, 20-gauge venous access will be established in all patients, and infusion with 2-4 mL/kg/h ringer's acetate solution will be started, general anesthesia will be induced with IV injection of fentanyl (1.5 µg/kg) (*Plaud et al., 2020*), propofol (2 mg/kg) (*Gelberg et al., 2014*) and atracurium (0.5 mg/kg) (*Plaud et al., 2020*) in the same sequence. Endotracheal intubation will be performed, controlled mechanical ventilation will be maintained to keep the end-expiratory carbon dioxide (CO₂) values between 34 and 36 mmHg using capnography. Anesthesia will be maintained with isoflurane 1-2 MAC in 40 % oxygen in air. Incremental dose of atracurium (0.1 mg/kg) (*Bhoi et al., 2019*) will be given after assessment by nerve stimulator according to train of four. Granisetron 3mg (*Dehghanpisheh et al., 2022*) (EM-EX[®] ,3mg/3ml, Amoun pharmaceutical company, Cairo, Egypt) will be also administered to prevent postoperative nausea and vomiting.

Intraoperative fentanyl 0.5 µg/kg (*Plaud et al., 2020*) will be given if the HR or the blood pressure or both increase by >20% of the baseline. At the end of the procedure Isoflurane will be discontinued, neuromuscular blockade will be antagonized by using neostigmine 0.04 mg/kg (*Choi et al.,*

2016) plus atropine 0.01 mg/kg (*Elnasr et al., 2019*) after assessment by nerve stimulator according to train of four and will be administered to reverse the effect of atracurium. After extubation, all patients will be transferred to the post-anesthesia care unit (PACU).

- **Postoperative settings:**

During the first 24 hr after surgery, Postoperative pain will be evaluated by VAS score at 0 point (on admission to the PACU), 2, 4, 8, 16 and 24 hours postoperatively and increments of intravenous meperidine 0.5 mg/kg (*Friesen et al., 2016*) (pethidine-HCL®, 50 mg/ml, Misr company for pharmaceuticals, Cairo, Egypt) will be given as a rescue analgesia at any time the patient feels any pain for a pain score more than 4 (maximum dose 600 mg per day) (*Friesen et al., 2016*), if the patient still in pain after using maximum dose meperidine per day, she will be given morphine 0.1 mg/kg (*ElGhamry and Amer, 2019*) (Morphine sulphate®, 10 mg/ml, Misr company for pharmaceuticals, Cairo, Egypt), considered block failure to be excluded from the study and replaced by another patient to fulfill sample size criteria.

In the presence of nausea, with or without vomiting, granisetron 3 mg (*Gelberg et al., 2014*) will be given IV and repeated once if nausea persisted (maximum dose of 6 mg per day) (*Gelberg et al., 2014*).

- Complications after puncturing of the blockade (hematoma in the puncture sites, pneumothorax, bradycardia defined as heart rate (HR) <50 beats/min, tachycardia defined as HR >110 beats/min, hypotension defined as a decrease in mean arterial pressure (MAP) of >20% from the baseline value and hypertension defined as an increase in MAP of >20% from the baseline value) will be evaluated and well-managed.

- **Outcome measurement:**

The age, weight, height, the American Society of Anesthesiologists (ASA) class of each patient will be recorded and compared among both groups.

- **Primary outcome:**

Post-operative pain severity assessed by VAS at 0 point (on admission to the PACU).

- **Secondary outcomes:**

1. Post-operative pain severity assessed by VAS at 2 hr, 4 hr, 8hr, 16 hr

and 24 hr.

2. Time of first rescue analgesia.
3. Cumulative post-operative meperidine consumption in the first 24 hours.

➤ **Statistical Analysis:**

All data will be recorded, analyzed and statistically compared between both groups to describe the groups and identify any significant differences between them. The quantitative data will be presented as mean \pm standard deviation and range. Qualitative data will be presented as a number and percentage. Non-parametric data will be presented as a median and inter-quartile range.

The following tests will be done:

- Independent samples t-test of significance will be used when comparing between two means.
- Mann Whitney U test: for two-group comparisons in non-parametric data.
- Chi-square (χ^2) test of significance will be used in order to compare proportions between qualitative parameters.
- The confidence interval will be set to 95% and the margin of error accepted will be set to 5%. So, the p-value will be considered significant as the following:
 - P-value <0.05 will be considered significant.
 - P-value <0.001 will be considered as highly significant.
 - P-value >0.05 will be considered insignificant.

➤ **Statistical package:**

Recorded data will be analyzed using the statistical package for social sciences, version 23.0 (SPSS Inc., Chicago, Illinois, USA).

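### The 90% power is planned on VAS at 1 hour, which is never measured; the primary outcome, VAS on PACU admission, has no planning figure and so no stated power.

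*Combined protocol and SAP*

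**What the plan says.** All references are to the combined protocol and SAP, section 3 (Methodology).

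- **Sample Size.** The calculation is described as "setting power at 90% and alpha error at 0.05". Its planning values, taken from a cited earlier trial of the same two blocks, are "the expected median VAS score 1-hour post-operative in PECS II group = 1(1-2) and in ESPB group= 2(1-3"). The conclusion is "Sample size of 10 patients per group will be needed to detect the difference between two groups".
- **Postoperative settings.** Pain is to be assessed by "VAS score at 0 point (on admission to the PACU), 2, 4, 8, 16 and 24 hours postoperatively". Rescue meperidine "will be given as a rescue analgesia at any time the patient feels any pain for a pain score more than 4".
- **Outcome measurement, Primary outcome.** There is one primary outcome: "Post-operative pain severity assessed by VAS at 0 point (on admission to the PACU").
- **Outcome measurement, Secondary outcomes.** The remaining VAS times are listed as "Post-operative pain severity assessed by VAS at 2 hr, 4 hr, 8hr, 16 hr" and 24 hours.

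No expected VAS value, difference or spread for PACU admission appears anywhere.

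**The concern.** A power statement describes one test, at one time, with an assumed difference and spread. Here those assumptions are for 1 hour after surgery, while the primary test is done on the PACU admission score. The protocol does not say that the two times are interchangeable, and its own schedule gives a reason to doubt it. The admission score comes before any postoperative rescue can act, whereas a 1-hour score may already reflect meperidine given for a score above 4. Neither the difference between blocks nor the spread can be assumed equal at the two times.

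What is at stake is how the result will be read. With 20 patients, a non-significant primary comparison is quite possible even if the blocks differ. The report would then cite 90% power that was never worked out for that comparison, and readers could take the result as evidence that the blocks are equivalent.

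**Working it through.** **1. Time points side by side**

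| Where | VAS time |
|---|---|
| Sample Size | 1 h |
| Primary outcome | 0 (PACU admission) |
| Secondary outcomes | 2, 4, 8, 16, 24 h |
| Assessment schedule (Postoperative settings) | 0, 2, 4, 8, 16, 24 h |

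The schedule and the outcome list agree with each other. Only the sample-size paragraph uses 1 hour. The mismatch is established at this step and does not depend on the arithmetic below.

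**2. The plan's own figure**

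Inputs from the Sample Size section: medians 1 and 2 (difference δ = 1), brackets 1-2 and 1-3, alpha 0.05, power 90%, 10 per group. The plan does not state what the brackets are, the SD, the number of sides, or which test was powered.

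Assumptions made here: the brackets are interquartile ranges, SD = IQR/1.35, and the difference in medians stands in for a difference in means.

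- PECS II: 1/1.35 = 0.74
- ESPB: 2/1.35 = 1.48
- Pooled: √((0.74² + 1.48²)/2) = 1.17

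Normal approximation, two-sided: n per group = 2 × (1.960 + 1.282)² × SD²/δ² = 21.0 × SD².

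- SD 0.74: 11.5, so 12
- SD 1.17: 28.8, so 29
- SD 1.48: 46.02, so 47

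Ten per group is not reproduced on the plain reading (pooled SD, two-sided). Some unstated choices come close. A one-sided test with the PECS II spread in both arms gives 2 × (1.645 + 1.282)² × 0.74² = 9.4, so 10. Whether 10 follows from the 1-hour inputs is thus a separate, unsettled question, and this point does not rest on it.

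**3. What 10 per group can detect (illustration only)**

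Two-sample t-test (noncentral t), two-sided alpha 0.05. At n = 10 per group, 90% power needs a standardised difference of 1.534.

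| Assumed SD | Power for 1 point, n = 10 | Detectable at 90% (1.534 × SD) | n per group for 90%, 1 point |
|---|---|---|---|
| 0.74 | 82% | 1.1 points | 12.6, so 13 |
| 1.17 | 44% | 1.8 points | 29.8, so 30 |
| 1.48 | 30% | 2.3 points | 47.01, so 48 |

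For 90% power at 1 point with 10 per group, the SD would have to be about 1/1.534 = 0.65 or less. At the pooled SD, a simulated Mann-Whitney test gives about 41%, close to the 44% by t-test.

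**4. The primary test**

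The power at PACU admission cannot be computed, because δ and SD are missing. To show how far it depends on them, take the normal approximation, power = Φ(δ/(SD × √(2/10)) − 1.96), with assumed SDs from 0.74 to 2:

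- δ = 0.5: 8% (SD 2) to 33% (SD 0.74)
- δ = 1: 20% to 86%
- δ = 2: 61% to above 99%

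Nothing in the documents places the trial within this range.

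**The case against.** The strongest reply is that a neighbouring time point is a common stand-in when no exact figure is available. Both readings are early postoperative VAS, on one scale, between the same two blocks. On that view the fault is an undeclared proxy, and the 90% is not shown to be wrong. That is fair as far as it goes: nothing shows the true power is lower. But the protocol neither declares nor defends a proxy, so the 90% has no support for the primary test.

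The illustration is also open to challenge. The brackets are not labelled, the number of sides is not stated, and the test for a VAS summarised by medians would probably be Mann-Whitney. A quartile-based mean, (q1 + median + q3)/3, gives 2 − 1.33 = 0.67 points and not 1. A one-sided t-test at SD 0.74 and n = 10 has 89.6% power, almost the stated figure. All of this stands as a limit on the illustration. None of it supplies a figure for PACU admission.

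A 95% confidence interval at PACU admission would still show which differences remain compatible with the data, whatever the planning basis. That is true, and it limits the harm. It does not supply the missing planned difference, or a basis for claiming 90% power.

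Finally, randomisation and the type I error of the primary test are untouched. That is correct; the defect lies in the justification of the sample size.

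**Conclusion.** The concern holds. The sample size and the 90% power rest on a 1-hour VAS comparison that is neither scheduled nor listed as an outcome, and the sole primary outcome has no planning difference, spread or stated power. This follows from the document alone and needs no assumption.

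The size of the effect on power cannot be calculated, and its direction is unknown. The 82%, 44% and 30% figures show only what 10 per group can detect for a 1-point difference if the 1-hour brackets are interquartile ranges and the test is a two-sided t-test. They should not be read as the loss caused by the mismatch. The point must be fixed because it concerns the only primary outcome and the only justification given for the sample size.

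**What to change.** Before any outcome data are seen, make the planning figure and the primary time point agree.

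- **Preferred: keep PACU admission as primary.** Replace the 1-hour values with an expected difference and SD for PACU admission and their source. Name the test and the number of sides. Then state the power that 10 per group delivers, or the difference detectable at 90%, in place of the present claim. The preference is a judgement: this reading is already scheduled and precedes postoperative rescue, although intraoperative fentanyl may still influence it. The cost is a rewording of the Sample Size paragraph, and the restated power may differ from 90%.
- **Alternative: make 1 hour primary.** Add a 1-hour VAS to the schedule and the outcome list, and restate the power there with the SD, test and number of sides given. Note that rescue meperidine can affect a 1-hour score, and that moving the time point does not by itself restore 90% power. The cost is one extra bedside reading plus wording.

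Neither route requires more patients. If the sponsor wants to keep 90% power, recruitment may rise: for a 1-point difference, to about 13, 30 or 48 per group at assumed SDs of 0.74, 1.17 or 1.48, instead of 10.

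### Patients still in pain after maximum meperidine are excluded and replaced after randomisation, so the worst analgesic results leave the comparison

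*Combined protocol and SAP*

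**What the plan says.** Study procedures, Preoperative settings: "Patients will be randomly divided according to a computer-generated random number table into two groups", with 10 patients in each. Allocation is therefore fixed before surgery.

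Postoperative settings: rescue meperidine is given in increments of 0.5 mg/kg for a pain score above 4, up to 600 mg per day. Beyond that, "if the patient still in pain after using maximum dose meperidine per day, she will be given morphine 0.1 mg/kg", and she is "considered block failure to be excluded from the study and replaced by another patient to fulfill sample size criteria".

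Outcome measurement: the primary outcome is VAS on admission to the PACU. The secondary outcomes are VAS at 2, 4, 8, 16 and 24 hours, time of first rescue, and "Cumulative post-operative meperidine consumption in the first 24 hours".

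The plan's general statement, under Statistical Analysis, is "All data will be recorded, analyzed and statistically compared between both groups to describe the groups". The section defines no analysis population. For quantitative outcomes it lists two tests, "Independent samples t-test of significance will be used when comparing between two means" and "Mann Whitney U test: for two-group comparisons in non-parametric data", without saying which applies to meperidine. Block failure by arm is not listed as an outcome, and no method is given for allocating a replacement.

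**The concern.** The exclusion comes after randomisation and is triggered by the outcomes being compared: persistent pain and the largest rescue use the protocol allows. In a trial whose aim is to compare analgesic efficacy, a failed block is the clearest evidence of poor efficacy, and this rule takes it out.

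The plan does not say in so many words that recorded values are deleted. But a replacement is needed to reach 10 per arm only if the failed patient no longer counts. If she leaves, so do her time to first rescue, her later VAS scores, her 24-hour meperidine at the maximum, and her PACU-admission VAS. That last value is the primary outcome and was recorded before failure could occur.

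If failures differ between arms, part of a true difference disappears. If they do not, the contrast is unbiased on average but both blocks look better than they are. The direction of any bias cannot be known in advance. An unspecified allocation for replacements is a further opening for selection.

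**Working it through.** The plan gives no failure rate and no expected meperidine use, so there is no figure of its own to reproduce on this point. What follows uses its 10 patients per arm, 0.5 mg/kg increment, 600 mg maximum and p < 0.05 criterion. Other inputs are marked as assumed.

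**1. How hard the trigger is to reach.** Increments needed = 600 / (0.5 × weight). At assumed weights of 50, 70 and 100 kg this is 24, 17.1 and 12 doses within a day. Failure is probably rare.

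**2. Chance that the rule is used at all.** P(at least one failure in 20) = 1 − (1 − p)^20, with p assumed.

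| p per patient | P(at least one) |
|---|---|
| 0.1% | 2% |
| 0.2% | 4% |
| 0.5% | 10% |
| 1% | 18% |
| 2% | 33% |
| 5% | 64% |

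One failure is 1/10 = 10% of an arm.

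**3. Effect on a rank comparison of 24-hour meperidine.** With 10 v 10 there are 100 pairs. Let U be the number of pairs in which the patient from the lower-use arm used more. Assume no ties, one failure only, and a replacement who joins the same arm and is typical of it. The failed patient wins all 10 of her pairs. Her replacement wins the average number won by the other nine in her arm.

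Exact two-sided p-values:

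| U | 14 | 15 | 22 | 23 | 24 | 25 | 26 | 30 |
|---|---|---|---|---|---|---|---|---|
| p | 0.0052 | 0.0068 | 0.0355 | 0.0433 | 0.0524 | 0.0630 | 0.0753 | 0.1431 |

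- *Failure in the higher-use arm, U = 23 with her included.* The arm wins 77 = 10 + 67, and 67/9 = 7.4. Replacement loses 2.6 wins, so U becomes about 25.6 (p between 0.063 and 0.075). Significance is lost.
- *Failure in the lower-use arm, U = 23.* The arm wins 23 = 10 + 13, and 13/9 = 1.4. It loses 8.6, so U becomes about 14.4 (p between 0.005 and 0.007). The result is made to look stronger.
- *Failure in the lower-use arm, U = 30.* The arm wins 30 = 10 + 20, and 20/9 = 2.2. It loses 7.8, so U becomes about 22.2 (p between 0.036 and 0.043). Significance is created from p = 0.143.

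*How wide these windows are.* For a failure in the higher-use arm, U = 22 moves to 24.4 (lost), 21 to 23.3 (borderline), 20 to 22.2 (kept) and 15 to 16.7 (kept). So significance is lost only near the boundary. Significance is created from starting values of about 24 to 30, and only when the failure is in the arm that otherwise uses less. Ties, for example several patients at 0 mg, would change the p-values.

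**4. Effect on means.** Replacing one 600 mg patient by one using c mg lowers the arm mean by (600 − c)/10. For assumed c = 0, 35 and 105 mg this is 60.0, 56.5 and 49.5 mg.

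**5. What keeping the failure does to spread.** Assume the other nine have mean 100 mg and SD 50 mg.

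- With a 100 mg replacement: SD = √(8 × 50² / 9) = 47 mg.
- With the failure kept: mean = (9 × 100 + 600)/10 = 150 mg. Sum of squares = 8 × 50² + 9 × 50² + 450² = 245,000, so SD = √(245,000/9) = 165 mg.

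**The case against.** The strongest reply is that the rule may never be used. It needs 600 mg of meperidine with pain persisting. The only pain levels the protocol expects, under Sample Size, are 1-hour VAS medians of 1 (1–2) and 2 (1–3). If the brackets are interquartile ranges, the upper quartiles of 2 and 3 lie below the rescue threshold. Rates of 1% to 5% have no source, and at equally unsourced rates of 0.1% to 0.5% the chance of any failure is only 2% to 10%. With no failure, nothing changes. This stands as a limit on size. It concerns a single time point, however, and does not justify the rule if a failure does occur.

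Second, the loss of significance shown above occurs only close to the boundary, and its creation needs the failure to fall in a particular arm. That is correct, and the windows are stated for that reason.

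Third, the primary outcome is taken before any postoperative rescue, so it is touched only by swapping one patient's value for another's. That also stands. All the arithmetic concerns a secondary outcome.

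Fourth, the Statistical Analysis section says all data will be analysed. That sentence is generic. It cannot restore a patient whom a specific rule excludes and replaces to make up the numbers. If the intention is to keep her values, the plan still has to say so.

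**Conclusion.** The concern holds. The protocol prescribes an outcome-dependent exclusion after randomisation, and nothing elsewhere in it keeps the excluded patients in an analysis. This should be fixed before the data are analysed.

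The practical size depends on an unknown and probably low failure rate. When a failure does occur, it removes 10% of an arm, lowers that arm's mean meperidine by roughly 50 to 60 mg under the assumed replacement values, and can change the significance of a result near the boundary. The main exposure is 24-hour meperidine and later VAS. The effect on the primary outcome cannot be quantified from the documents. The conclusion rests on reading exclusion and replacement as removal from the analysis, which is the natural sense of the text.

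**What to change.** Leave rescue treatment as written and change only the study and analysis wording:

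- A patient classed as a block failure stays in the study and is not replaced. Every randomised patient is analysed in her assigned arm.
- Her PACU-admission VAS, time to first rescue and all other values before failure are used as recorded, and her records continue to 24 hours.
- Block failures are reported by arm.
- The handling of later VAS and 24-hour meperidine after failure is pre-specified. One option is to assign the worst rank (tied if several fail) in a Mann-Whitney test, with values as recorded as a sensitivity analysis. That sensitivity analysis should note that meperidine alone does not count the morphine she received.
- Any analysis that leaves failures out is labelled as a sensitivity analysis.

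The cost is a wording amendment and complete 24-hour records for failed patients. No replacements need to be recruited. The downside is more variable meperidine data, substantially so with means and a t-test (SD about 165 mg against 47 mg in the illustration). A rank-based comparison, already among the listed tests, is therefore preferable for that outcome.
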